3.2 Overview of the interventions

SHIELD intervention. The SHIELD intervention is based on social cognitive theory, which posits that positive behavior change requires knowledge and skills to increase behavioral capability, development of self-efficacy to increase the belief that one can achieve the desired outcomes, and social support to provide positive reinforcement and develop positive outcomes expectations.⁴⁶ We developed a modular program for AGYW that increases knowledge, skills, and self-efficacy to engage along the HIV prevention and care continuum, and a program for family members (up to four participants in addition to the AGYW; 10 years and older) to increase social support. To reflect AGYW's evolving cognitive and decisional capacity, judgement, emotional development, risk, and health-seeking behaviors, intervention content for both AGYW and families were tailored for five distinct groups to reflect development stage and

AGYW's HIV status. Content areas were adapted from existing evidence-based interventions, such as Stepping Stones^{30,31} and Families Matter!^{47,48} based on CAB and YAB input and formative research with AGYW, caregivers, and community leaders. Modules address HIV prevention and treatment, general wellness and SRH, approaches to combat stigma and discrimination, and skills for better communication, and include new content on health service availability and access to increase self-efficacy in seeking health care services. SHIELD educational materials were pre-tested. The SHIELD sessions will be offered to AGYW and their families in the 4 communities randomly assigned to intervention arms. The AGYW in the usual care arm will receive one education session focused on stigma and HIV care. SHIELD education session content is presented in **Exhibit 1** for the AGYW sessions and **Exhibit 2** for the family sessions. We have noted content that will be included in core sessions along with content that will be included in the basic education provided to the control group participants. The core sessions will be provided to all participants in the intervention communities while all other sessions will be optional content for future meetings within the intervention communities.

Exhibit 1. SHIELD Content Areas for Adolescent Girls and Young Women Program

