| AGYW and Families | 
 1. What you see in me (All) 2. Making puberty easier (parents of AGYW ages 10-12) 3. HIV, AIDS and STIs- Myth or Fact (All)* 4. Helping children express their feelings (ages 10-12) 5. Taking responsibility for pregnancy: Community responsibility (ages 13-24)* | 
 1. Non-verbal communication (All) 2. Sharing information with family members: challenges and possibilities (HIV+ ages 16-24)* 3. Providing emotional support after a child learns that you or they are HIV positive (All) 4. Analyzing stigma against AGYW (All)* |

* Indicates core topic area

IWC Clinic

The Integrated Wellness Care (IWC) clinic for AGYW will be established in 2 randomly selected health centers participating in this study communities. The clinic will provide integrated HIV and sexual and reproductive health services to both participating HIV-/u and HIV+ AGYW facilitated by a trained nurse. Specifically, the IWC clinic will offer:

- HPV vaccination
- HIV testing & counselling
- ART adherence counselling (HIV+ AGYW)
- STI services information
- Family planning, including counselling, initiation of contraception, services related to current contraception, and pregnancy testing and counselling.
- Information on cervical cancer screening
- Referrals for services, such as mental health, gender-based violence, STI testing, cervical cancer screening, and other health services as needed

All services will be provided based on the standard of care guidelines and delivered by a trained nurse. IWC components and data collection was tested during the pilot-testing phase. In addition, selected staff at the health centers with the IWC clinic will receive stigma training to ensure team-based care is available for AGYW who are referred from the IWC clinic to received services in other departments at the health center. The training section includes four modules (2-hour session for each) that experienced trainers will deliver to give staff the skills to create a stigma-free health facility.^{29,30}

Caregiver and provider support for AGYW. We will include caregivers who will participate with AGYW in the SHIELD family sessions. We will identify one caregiver for each participating AGYW in the 6

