The sample size was calculated assuming conventional specifications (power = .80, alpha = .05, two-sided tests) and based on the primary endpoints. The sample sizes were determined to allow for the detection of a 15–percentage point improvement in the primary endpoints, our minimum threshold to consider the intervention to be successful. For the HIV-/u cohort, the current rate of HIV testing is estimated to be about 40%. With a sample size of 200 (each of the three cohorts), The study team will be able to detect a 13 to 14% difference, and even with a loss of 10% of the cohort during follow-up (the grant team achieved a 90% retention rate at 12 months in a recent study of AGYW),²⁸ the study team

will still have the statistical power for a minimum detectable difference in HIV testing of 15%. For the HIV+ cohort, viral load suppression is estimated to be 70 to 75% among AGYW. With a sample size of 175 per cohort, the study team will be able to detect a minimum difference of 15% even with a 10% loss to follow up. See **Exhibit 3** for details on sample size included in the cluster randomized trial.

Exhibit 3. Experimental design and sample sizes*

Post-intervention data collection: We will conduct one post-intervention survey with AGYW at about 24-months from study initiation (approximately 12 months after intervention completion).

Research Protocol

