Assess efficacy of the multilevel interventions (hypothesis testing). Cluster randomization study design and interventions. We propose a cluster randomized study implemented in the six selected geographic zones in Lusaka, each served by a government-operated clinic providing HIV and cervical cancer screening services. Zones, with their respective clinics, will be randomized into three groups (zones with IWC clinics and SHIELD intervention, zones with only SHIELD intervention, and control zones with no IWC clinic or SHIELD interventions. AGYW in the control zones will be offered one education session on HIV prevention and treatment) to assess the impact of offering IWC clinics coupled with the SHIELD intervention compared to the standard of care (see Exhibit 1 above). The study team will also evaluate whether a similar impact can be achieved with control clinics when the SHIELD intervention is offered in the community. The SHIELD intervention, as described in Section 3.2, will begin with training sessions for AGYW and their families. This will be followed by PN-facilitated youth clubs that will meet about once a month during the 12-month study timeframe. Two-four PNs will be assigned to each clinic zone with the SHIELD intervention, and one-two PN each will be assigned to the two control clinic zones to assist with data collection and follow-up activities. The PNs in zones with the IWC clinics will also serve as community liaisons to support clinic-community linkages. The health centers in which the **primary endpoint for the HIV/u cohort** is the proportion with any HIV testing at 12 months. **For the HIV+ cohort, we plan to assess the primary endpoint:** viral load suppression, measured as proportion with undetectable viral load at 12 months. The secondary endpoints are the proportion with decrease in HIV risk behavior, repeat HIV testing (each 6-month period), HIV infections diagnosed through voluntary HCT, linkages to HIV care, and adherence to ART. We will also conduct a targeted 6-month post-intervention data collection after the end of the 12-month intervention period. See **Exhibit 4** for endpoint definitions and biological, self-report, and clinic audit measures collected at 6- and 12-month follow up. To assess the impact of the SHIELD intervention on the mediating outcomes, the study team will collect data from AGYWs across all six clinic zones at baseline and at 6- and 12- month follow-up. The study team will also track health care service use by conducting clinic audits at all six clinic sites. We plan to retain the intervention cohort for a maximum of 24 months total to allow for initiation of the intervention and follow-up activities (12 months of intervention and follow-up after intervention completion).

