Hypotheses on intervention effect. The study team will test the following hypotheses: (1) HIV-/u AGYW from zones with IWC clinics and who receive SHIELD intervention will have higher HIV testing than AGYW in zones without the IWC clinics (including those receiving SHIELD intervention with usual care clinics); (2a) HIV+ AGYW from zones with IWC clinics and who receive SHIELD intervention will have higher viral load suppression (2b) than AGYW in zones without the IWC clinics (including those receiving SHIELD intervention with usual care clinics); (3) HIV+ AGYW from zones with IWC clinics will receive more-timely linkages to care than AGYW in zones without a IWC clinic; (4) AGYW from zones who receive SHIELD intervention will have improved self-efficacy (4a) and social support (4b), and reduced HIV risk behaviors (4c) compared to AGYW from zones not receiving the intervention.

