Analysis of hypotheses. The **testing of the primary hypotheses** will be done by intent to treat, and the study team will examine the effects across the three randomization groups. Given the need to consider the influence of the cluster randomization by zone, The study team will use generalized estimating equation (GEE) models to estimate the effects of the randomization groups and will assess the need to apply small sample correction using approaches suggested by the NIH Health Care Systems Collaboratory Biostatistics and Design Core.⁵⁹ If the Hausman assumption of correlation between the random and fixed effects is violated, then The study team will include fixed effects representing cluster identification. The study team will adjust for baseline covariates, including sociodemographic factors and behavioral risks, should the initial descriptive analyses suggest differences in the distribution of these factors across study randomization groups. The study team will also explore the use of propensity scores to control for systematic differences between the groups. In further analyses, the study team will examine the potential mediating and moderating roles of key behavioral, social, and structural factors hypothesized to influence HIV testing and adherence along the HIV care continuum (e.g., social support; self-efficacy).. The study team will test the “dose” of the SHIELD training received as a covariate in these models. **Secondary analysis** will follow the same approach. As appropriate, the study team will perform analyses separately or pooled together for the HIV+ and HIV-/u cohorts. A key aspect of interest in this study is the developmental stage of the AGYW; using age as a proxy in our multivariate analysis, the study team will determine the differential effect of the IWC clinic and SHIELD intervention on outcomes reported by HIV status (see Exhibit 1 for groupings). In subsequent analyses, the study team will also consider both medium-term outcomes within the first 6 months after study enrollment and changes at any point during the 12-month follow-up period to assess longer-term outcomes. Additionally, for measures where we have baseline, 6-month and 12-month follow-up data (for example, self-efficacy, and other mediating outcomes for AGYW), the study team will perform difference-in-difference analysis, which will allow for comparisons between and across the study arms. The study team will also report all mediating factors, and 'IWC clinic utilization metrics stratified by age and HIV status to facilitate subgroup analysis. Importantly, the changes along the HIV care cascade, from HIV testing, linkage to care, ART adherence, and viral load suppression, will be documented to identify potential differential impacts of the interventions. This analysis is critical to assist in further tailoring the SHIELD training and IWC clinic services.

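### The small-sample correction of the primary GEE is left optional with two zones per arm; if it is omitted and normal quantiles are used, type I error is about 23–30%, not 5%

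*Combined protocol and SAP*

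**What the plan says.** All references are to the combined protocol and SAP.

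- **Design.** SHIELD is offered "in the 4 communities randomly assigned to intervention arms" and the IWC clinic "will be established in 2 randomly selected health centers" (section 3.2). Peer navigators "will be assigned to the two control clinic zones" (section 3.3, Research Protocol). Six zones in three groups therefore means two zones each for IWC plus SHIELD, SHIELD only, and control.
- **Hypotheses.** Hypothesis 1 is that HIV-/u participants in IWC zones "will have higher HIV testing than AGYW in zones without the IWC clinics", and the comparison expressly includes the SHIELD-only zones. Hypothesis 2 has the same form for viral suppression. Both compare 2 zones with 4. The Research Protocol text also describes IWC plus SHIELD against standard of care, which is 2 zones against 2.
- **Analysis.** Under Analysis of hypotheses, the team will "examine the effects across the three randomization groups" by intention to treat with GEE, and "will assess the need to apply small sample correction using approaches suggested by the NIH Health Care Systems Collaboratory" (reference 59). If a Hausman check fails, the team "will include fixed effects representing cluster identification". Secondary analyses follow the same approach.
- **Error rate and power.** The sample-size text states "power = .80, alpha = .05, two-sided tests" for a 15-point improvement.

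The plan does not fix the mean model (three arms, or IWC against the rest), the variance estimator, the reference distribution, the degrees of freedom, or a rule for judging whether correction is needed.

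**The concern.** The GEE sandwich variance is justified by a large number of clusters. Here each arm mean rests on two zones, so its uncorrected robust variance averages half the true value, and the estimated variance is itself very unstable. The first problem calls for a corrected variance, the second for a t reference with few degrees of freedom. The wording permits neither, or only one, and leaves the choice until the data are in hand.

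The choice governs both primary endpoints. The protocol also says that if the intervention succeeds, the Ministry of Health will advocate for expansion to support national scale-up, so a false positive would have consequences.

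The Hausman fallback raises a second problem. Each zone belongs to one arm only, so zone indicators absorb the arm effects that the trial was designed to estimate.

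**Working it through.** **Inputs.** From the sample-size text: two-sided alpha 0.05, power 0.80, 200 per arm (HIV-/u) and 175 per arm (HIV+), base rates 40% and 70–75%, 10% loss, 15-point target. From sections 3.2 and 3.3: six zones, two per arm. Assumed: equal zones of 90 (200/2 less 10%) or 79 (175/2 less 10%), and ICC 0 to 0.05. The ICC barely affects the type I error.

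**1. The plan's own figure.** For two independent proportions, n = [1.96·√(2p̄q̄) + 0.842·√(p₁q₁ + p₂q₂)]² / d². For 40% v 55% this is (1.384 + 0.588)² / 0.0225 = 173 per arm. Solving for d gives 13.9 points at n = 200 and 14.7 points at n = 180. These match the stated 13–14% and 15%, so the plan's figure is reproduced by a calculation that ignores clustering.

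**2. Uncorrected test, 2 v 2.** The robust variance of an arm mean is (sum of squared zone deviations)/2², half the unbiased value. The robust z is therefore √2 times a t on 2 df. Since P(|t₂| > x) = 1 − x/√(2 + x²), putting x = 1.96/√2 = 1.386 gives 1 − 1.386/1.980 = **30.0%**. This is exact for normal zone means with equal zones.

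**3. Corrected variance, normal quantiles, 2 v 2.** Kauermann-Carroll (KC) doubles the variance: x = 1.96 gives 1 − 1.96/2.417 = 18.9%. Mancl-DeRouen (MD) quadruples it: x = 1.96·√2 = 2.772 gives 1 − 2.772/3.112 = 10.9%.

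**4. All settings** (2 v 4 by simulation of normal zone means, no effect):

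| Method | 2 v 2 | 2 v 4, three-arm contrast |
|---|---|---|
| Uncorrected, normal quantiles | 30.0% | 28.3% |
| KC, normal quantiles | 18.9% | 16.7% |
| MD, normal quantiles | 10.9% | 8.5% |
| MD, t on 3 df | 4.6% | 2.7% |
| Zone summaries, variance pooled over three arms, t on 3 df | 5.0% | 5.0% |

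If the four non-IWC zones are coded as one group, the uncorrected 2 v 4 figure is 23.0% when SHIELD alone has no effect. It falls to 21%, 17% and 12% if SHIELD alone adds 5, 10 or 15 points (ICC 0.01, IWC arm at the average of the other two), because the gap between those arms then inflates the variance estimate. Beta-binomial simulations with equal zones agree with the uncorrected figures (about 30%, 28% and 23%). Zone sizes in a 0.7:1.3 ratio raise them to 31–34%, 30–33% and 24–26%.

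**5. Limit of the pooled zone-level test.** The 5.0% needs equal between-zone variance across arms. If the IWC-arm variance is doubled, the error is 6.1% (2 v 2) and 6.9% (2 v 4). If it is quadrupled, 8.0% and 9.7%. These ratios are assumptions.

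**6. Fixed-effects fallback.** Six zone indicators plus two arm indicators make eight columns of rank 6. The two arm effects cannot be separated from the zones.

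**7. Power of a valid test**, 40% v 55%, ICC 0, 90 per zone, critical value 3.182:
- 2 v 2: SE = √(0.24/180 + 0.2475/180) = 0.0520; noncentrality 0.15/0.0520 = 2.88; power about 50%.
- 2 v 4, SHIELD-only zones at the control rate: SE = √(0.2475/180 + 0.24/360) = 0.0452; noncentrality 3.32; power about 61%.

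At an assumed ICC of 0.01 these fall to about 31% and 39%.

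**The case against.** The plan recognises the cluster design, names the small-sample problem and cites a source for handling it. To reach 23–30% the team would have to judge correction unnecessary and then use normal quantiles, and nothing in the plan names a z test. Reference 59 cannot be read here and may call for correction with so few clusters. This stands: what is established is under-specification. A reader might infer that this trial's type I error is 30%. The documents do not support that, because a team that corrects variance and df together can hold about 5%.

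Three other strong readings also go too far:

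- *That 28–30% applies to both primary hypotheses.* Hypotheses 1 and 2 are 2 v 4 comparisons, and since no mean model is fixed, 23% under two-group coding is equally possible. The 30% belongs to the 2 v 2 comparison.
- *That zone fixed effects must never be used for between-arm questions.* The plan also intends difference-in-difference analyses for measures with baseline data. Arm-by-time effects remain estimable there with zone fixed effects.
- *That the plan contains no ICC.* The readable text gives none, but the content of Exhibit 3 and the note behind its asterisk are not shown.

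The objection does not remove the core point. An assessment of need has only one sound outcome with two zones per arm, and the wording would also be met by a corrected variance with normal quantiles, which is not enough.

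**Conclusion.** The concern holds in a conditional form and should be fixed before the primary results are relied on. With equal zones, leaving out the correction and using normal quantiles gives a type I error of about 23–30% depending on the contrast and mean model. A corrected variance with normal quantiles gives about 8–19%. These are the worst cases that the wording permits, not the error rate of a plan that corrects fully. They rest on equal zone sizes, exchangeable zones under no effect and no covariate adjustment.

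Two conclusions do not depend on that condition. The zone fixed-effects fallback cannot yield 12-month arm main effects. And the stated 80% power fits an unclustered calculation: a zone-level test on 3 df has about 50% (2 v 2) or 61% (2 v 4) for 40% v 55% even at ICC 0, and less at any positive ICC.

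**What to change.** - **Commit to one method.** In Analysis of hypotheses, replace the promise to assess the need with a single named small-sample method for every between-arm test and confidence interval, fixing mean model, variance estimator and df together. Either of these would serve:
  - one summary per zone, variance pooled over the three arms, t on 6 − 3 = 3 df, with the equal-variance condition stated; or
  - a three-arm GEE with Mancl-DeRouen variance and t on 3 df, which is conservative for 2 v 4.
- **Check it** by simulation at the actual zone sizes, including unequal between-zone variances.
- **Narrow the Hausman rule.** Drop zone fixed effects for arm main effects on endpoints without a baseline measure, and leave the difference-in-difference analyses as they are.
- **Restate power** for the chosen test, with an explicit ICC or range.
- **Date the change.** Section 3.1 describes the trial in the past tense. If outcomes by arm have been seen, label the change post hoc.

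**Cost.** Text and code only; no new data. Precision and stated power fall. For HIV testing, 2 v 2 at ICC 0, SE = √(2 × 0.24/180) = 0.0516, so the 95% interval is ±16 points (× 3.182) instead of ±10 (× 1.96). At an assumed ICC of 0.01, SE = 0.0516 × √(1 + 89 × 0.01) = 0.0710, giving ±23 instead of ±14. The narrower intervals are not a real gain, since their coverage is below 95%.

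### Adding zone fixed effects as a fallback leaves the primary model with no identifiable arm effect, because arm is assigned by zone

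*Combined protocol and SAP*

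**What the plan says.** Section 3.3 (Research Protocol) sets the unit of allocation: "We propose a cluster randomized study implemented in the six selected geographic zones in Lusaka", and "Zones, with their respective clinics, will be randomized into three groups". Two zones per group follows from three statements. SHIELD is offered "in the 4 communities randomly assigned to intervention arms" (section 3.2), IWC clinics "will be established in 2 randomly selected health centers participating in this study communities" (section 3.2), and "one-two PN each will be assigned to the two control clinic zones" (section 3.3).

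Under Analysis of hypotheses in section 3.3, the team "will use generalized estimating equation (GEE) models to estimate the effects of the randomization groups", with zone named as the level of clustering. The fallback comes in the same primary-hypothesis text. If a Hausman condition on the random and fixed effects is violated, "then The study team will include fixed effects representing cluster identification". Secondary analyses are to follow the same approach.

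Both primary endpoints are proportions at 12 months: any HIV testing (HIV-/u cohort) and undetectable viral load (HIV+ cohort). Exhibit 4 lists both measures at 6 and 12 months (HIV testing also by self-report at 24 months), and neither at baseline. Difference-in-difference analysis is planned for measures that have baseline, 6-month and 12-month data, with self-efficacy and other mediating outcomes as examples.

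**The concern.** A regression can separate an arm effect from zone effects only if arm varies within zones, and here it does not. Once every zone has its own parameter, nothing is left for an arm parameter to explain. The branch removes the quantity that the primary analysis exists to estimate.

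The trigger does not fit the model either. A Hausman test compares random-effects and fixed-effects estimates of the same coefficient. A GEE has no random effects, and in the fixed-effects model the arm coefficient does not exist. Nor is there a problem for the test to solve where arm is concerned: allocation is random, so zone effects are independent of arm by design.

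Two things are at stake. Followed literally, the branch gives either no primary result or an arbitrary contrast of single zones reported as the treatment effect. And because the choice of model would depend on observed outcome data, the primary analysis would not be fixed in advance.

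**Working it through.** The plan gives no figure for this point. Its sample-size figure (13 to 14 points detectable with 200 per arm from 40%) reproduces at 13.9 points as an individually randomised calculation, but nothing below depends on it.

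**Inputs.** Six zones, three arms, two zones per arm, arm constant within zone (sections 3.2 and 3.3). The endpoint is measured once, at 12 months.

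**Step 1: the identity.** Label the zones a to f, with a and b in the IWC plus SHIELD arm, c and d in the SHIELD-only arm, and e and f as control. For every participant,

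- arm indicator 1 = Z_a + Z_b
- arm indicator 2 = Z_c + Z_d

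So adding a constant to the first arm effect and subtracting it from zones a and b leaves every fitted value unchanged. The same holds for the second arm. There are two free constants and hence two redundant columns.

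**Step 2: rank.** Columns: 1 intercept + 5 zone dummies + 2 arm terms = 8. There are only six distinct rows, one per zone, and the rank is 6 = 8 - 2. Regressing each arm indicator on the zone dummies leaves a residual sum of squares of 0 (about 1e-28 numerically). A null-space check confirms that neither arm coefficient is estimable. An individual covariate such as age gives 9 columns and rank 7, with the same two deficiencies. Sample size per zone is irrelevant. Without zone dummies the arm model has full rank (3 of 3), with 6 - 3 = 3 between-zone degrees of freedom.

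**Step 3: what software might report.** One dataset was simulated with 100 per zone. True rates were 35% and 45% (reference arm), 40% and 42% (second arm), and 38% and 46% (third arm), so the true arm means are 40%, 41% and 42%. Linear fits with different zone dummies retained gave:

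| Zones left as references (reference, second, third arm) | Second vs reference arm | Third vs reference arm | Residual SS |
|---|---|---|---|
| first, first, first | +0.18 | +0.11 | 143.57 |
| second, second, second | -0.06 | -0.03 | 143.57 |
| first, second, first | +0.13 | +0.11 | 143.57 |
| second, first, second | -0.01 | -0.03 | 143.57 |

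The fit is identical each time. The printed effect is simply the difference between the single zones left as references. A logistic GEE with all eight columns did not converge: the aliased coefficients were about 1e10 and most standard errors were undefined.

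**Step 4: where zone fixed effects do work.** With a baseline and one follow-up period, adding one time term and two arm-by-time terms gives 11 columns and rank 9. The arm-by-time terms are estimable and the arm main effects are not. With three periods there are 14 columns and rank 12, with the same conclusion. A baseline measurement therefore rescues a difference-in-difference estimand. Data at 6 and 12 months alone would identify only the difference in change between those visits, not the 12-month arm effect.

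**The case against.** The strongest reply is that the six zone means stay estimable. A pre-written contrast, such as the mean of the two IWC zones minus the mean of the two control zones, could be taken from a zone-dummy model. That is correct. In the simulated data, averaging the first two table rows gives (0.18 - 0.06)/2 = 0.06 and (0.11 - 0.03)/2 = 0.04. But the plan specifies no such contrast, and its standard error would reflect only variation within zones. The documents give no intracluster correlation. Assume 0.01 to 0.05 and 90 per zone (200/2, less 10%). The true variance then exceeds the reported one by a factor of 1 + m × ICC/(1 - ICC):

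- ICC 0.01: 1 + 90 × 0.01/0.99 = 1.91. The critical value shrinks to 1.96/√1.91 = 1.42, so the type I error is about 16%.
- ICC 0.05: 1 + 90 × 0.05/0.95 = 5.74. The critical value shrinks to 1.96/√5.74 = 0.82, so the type I error is about 41%.

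This route replaces a missing estimate with an invalid test.

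Second, the harm is conditional. The default GEE with arm terms is sound on this point, and an undefined trigger may never be invoked. That stands as a limit on the consequence. It does not justify keeping a rule that cannot be applied and leads to an unusable model.

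Third, section 3.3 says abstractors will take information from clinic records at baseline, so some baseline HIV-testing data may exist. That is possible for HIV testing. For viral load, Exhibit 4 gives a biological source, not clinic audit. No arm-by-time model is specified for either primary endpoint.

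**Conclusion.** The concern holds. If the fallback is used for a 12-month endpoint, no arm coefficient is identifiable: rank is 6 against 8 columns, and both arm contrasts are lost. The result rests only on arm being constant within zone, which the randomisation guarantees. It does not depend on sample size, covariates, link function or the two-per-arm split. It affects both primary endpoints and any secondary comparison of arms at follow-up analysed the same way.

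It does not affect the difference-in-difference analyses of measures with a baseline. Nor does it affect coefficients for factors that vary within zones, such as age or SHIELD dose, though those are not the intention-to-treat contrast. The simulated values in the table illustrate arbitrariness and do not predict this trial's results. The 16% to 41% range rests on assumed intracluster correlations.

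**What to change.** Delete the Hausman and fixed-effects sentence for every analysis that compares arms at follow-up, and replace it with text to this effect:

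> Models comparing randomisation groups at follow-up will include group terms and no zone indicators. Zone is the clustering unit in every model. Differences between zones will be addressed through individual-level baseline covariates named in advance. Zone fixed effects will be used only in difference-in-difference analyses of measures with a baseline, where the estimand is the group-by-time interaction.

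The clustering can be handled by a working correlation, a random intercept or a cluster-level summary. The plan should name one as primary, so that the choice is not made on the data. Keeping the planned GEE is the smallest change. Whichever is named, the text should acknowledge the 3 between-zone degrees of freedom.

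The cost is a few lines of analysis text, with no new data or recruitment. Section 3.1 describes the trial in the past tense, and the front matter notes updates in July 2025. The change should therefore be dated, with a statement of whether outcome data by arm had been seen.
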